8.3.6. Relationship to TRC105 Study Drug/Axitinib

In this study, TRC105 study drug is given in combination with Axitinib. The relationship of an adverse event to TRC105 study drug and axitinib should be classified by the Investigator using the following guidelines:

- Suspected Adverse Reaction to TRC105 (Arm B only): There is a reasonable possibility that TRC105 caused the adverse event (i.e., there is evidence to suggest a causal relationship between TRC105 and the adverse event).
- Suspected Adverse Reaction to axitinib (Arm A or B): There is a reasonable possibility that axitinib caused the adverse event (i.e., there is evidence to suggest a causal relationship between axitinib and the adverse event)

-
- Not Related: There is no reasonable possibility that the adverse event is associated with TRC105 study drug or axitinib.

AE's maybe related to both drugs. AE's related to TRC105 study drug or Axitinib are considered Adverse Drug Reactions (ADR).

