The best response (CR, PR, SD or PD according to RECIST 1.1 and according to Choi criteria) for each patient with measurable disease who received at least one dose of study drug will be listed by cohort and response rate (CR or PR) between the two arms will be compared by Chi-square test or Fisher exact test. Stable disease will be defined as lack of tumor progression lasting for 2 cycles or longer. Additional analysis will be conducted based on duration of response, defined from the time to first response (CR or PR) to disease progression and will be compared between arms using Kaplan Meier methods. Other secondary analysis would include disease stability rate (DSR) defined as the percent of subjects in ITT population with CR, PR and SD at 12 weeks, and will be compared by Chi-square test or Fisher exact test.

All AEs with an onset after initiation of treatment will be considered as treatment-emergent AEs. A preexisting condition that worsens during the treatment period will also be considered as a treatment emergent AE. All AEs will be coded by system organ class (SOC) and preferred term using NCI CTCAE (MedDRA) version 4.0.

The number and percentage of patients with the following types of treatment-emergent AEs will be summarized for each study arm: common and serious AEs, AEs related to study medication, AEs resulting in study discontinuation, and clinically significant laboratory abnormalities. Laboratory data will be summarized for baseline, treatment visits and change from baseline as appropriate for each arm. Non-treatment-emergent serious AEs will be described separately. Deaths will be reported with demographic information. Comparison of categorical values will be made by Chi-square or Fisher exact test and of continuous variables will be made by Student t test.

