12.2. Adverse Events

All AEs with an onset after initiation of treatment will be considered as treatment-emergent AEs. A preexisting condition that worsens during the treatment period will also be considered as a treatment emergent AE. All AEs will be coded by system organ class (SOC) and preferred term using NCI CTCAE (MedDRA) version 4.0.

The number and percentage of patients with the following types of treatment-emergent AEs will be summarized for each study arm: common and serious AEs, AEs related to study medication, AEs resulting in study discontinuation, and clinically significant laboratory abnormalities. Laboratory data will be summarized for baseline, treatment visits and change from baseline as appropriate for each arm. Non-treatment-emergent serious AEs will be described separately. Deaths will be reported with demographic information. Comparison of categorical values will be made by Chi-square or Fisher exact test and of continuous variables will be made by Student t test.

For the phase 1b portion treatment-emergent AEs will be summarized by dose level. For the phase 2 portion treatment emergent AEs will be summarized by treatment group. Treatment-emergent is defined as all events starting during or after the first dose of study drug (or axitinib) until 28 days following the last dose of study drug or axitinib, whichever is later. The number and percentage of patients with AEs will be displayed by SOC and PT. Summaries will be provided of AEs by grade and of AEs by relationship to study medication. Serious AEs, AEs leading to study discontinuation, AEs resulting in dose delay, and AEs with an outcome of death will be summarized and listed.

For the phase 1b portion, a summary table and listing will also be provided for DLTs.

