Appendix 1: Planned 105RC101 Tables

Appendix 2: Planned 105RC101 Listings

Separate tables and listings will be generated for the phase 1b and phase 2 portion of the study.

18. References

2. NCI Common Terminology Criteria for Adverse Events (CTCAE), Version 4.0.
http://www.acrin.org/Portals/0/Administration/Regulatory/CTCAE_4.02_2009-09-15_QuickReference_5x7.pdf
3. MedDRA: Medical Dictionary for Regulatory Activities terminology. Version 14.1. Reston, VA: Northrop Grumman, MedDRA MSSO.

19. Appendix 1 Tables

19.1. Tables in Text Phase 1b:

- Protocol Versions under which Each Patient was Treated
- Disposition of Patients by Treatment Group
- Incidence of Protocol Deviations by Treatment Group
- Demographics and Baseline Characteristics
- Screening ECOG Performance Status
- Past Cancer Treatment
- Primary Cancer Diagnoses by Dose Group
- Disease Present at Screening
- Best Overall Response and Duration of Response
- Summary of Serum TRC105 Pharmacokinetic Parameters Following Multiple Intravenous Infusions of TRC105
- Most Common ($n > 1$) and all Grade 3 and 4 Adverse Events by System Organ Class, by Preferred Term and by Grade and Dose Level
- Most Common ($N > 1$) and all Drug-Related Grade 3 and 4 Adverse Events by System Organ Class, by Preferred Term and by Graded Full Analysis Population and Dose Level
- Anti-Product Antibody (APA)

19.2. Appended Tables Phase 1b:

- 14.1. Demographic Data Summary Figures and Tables
 - 14.1.1. Patient Disposition
 - 14.1.3. Concomitant Medications
 - 14.1.4. Extent of Exposure to TRC105
 - 14.1.5. Extent of Exposure to Axitinib
- 14.2 Efficacy Data Summary Tables and Figures
- 14.3. Safety Data Summary Figures and Tables
 - 14.3.1. Displays of Adverse Events
 - 14.3.1.2. Number (%) of Patients with Treatment-Emergent Adverse Events
 - 14.3.1.3. Dose Limiting Toxicities
 - 14.3.1.4. Treatment-Emergent Adverse Events by Maximum CTCAE Grade
 - 14.3.1.5. Treatment-Emergent TRC105 Drug-Related Adverse Events by Maximum CTCAE Grade
 - 14.3.1.6. Treatment-Emergent Axitinib Drug-Related Adverse Events by Maximum CTCAE Grade
 - 14.3.1.7. Number (%) of Patients with Serious Treatment-Emergent Adverse Events

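### The Phase 2 between-arm comparison of drug-related AEs is not like for like: Arm B events can be attributed to either of two drugs, Arm A events to one

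*SAP*

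**What the plan says.** SAP 12.2 names the AE groups to be counted by patient in each arm: "common and serious AEs, AEs related to study medication, AEs resulting in study discontinuation, and clinically significant laboratory abnormalities". The paragraph ends: "Comparison of categorical values will be made by Chi-square or Fisher exact test and of continuous variables will be made by Student t test". It gives no significance level or sidedness and excludes no AE group. Protocol 10.5.2 has the same content for Phase 2, opening with "The number and percentage of patients with the following types of treatment-emergent AEs will be summarized for each study arm".

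Protocol 8.3.6 sets the attribution categories. One is "Suspected Adverse Reaction to TRC105 (Arm B only): There is a reasonable possibility that TRC105 caused the adverse event". Another is "Suspected Adverse Reaction to axitinib (Arm A or B): There is a reasonable possibility that axitinib caused the adverse event". The section allows an event to be related to both drugs and treats an event related to either one as an adverse drug reaction.

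The table lists differ between the two parts of the study. For Phase 1b, SAP 19.2 plans a TRC105-related table (14.3.1.5) and an axitinib-related one (14.3.1.6, "Treatment-Emergent Axitinib Drug-Related Adverse Events by Maximum CTCAE Grade"). The Phase 2 list in SAP 19.4 goes from 14.3.1.4 to 14.3.1.7 and contains neither. The Phase 2 in-text list (SAP 19.3) has one drug-related AE table that names no drug.

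SAP 12.2 also plans all-cause displays by treatment group: AEs by system organ class and preferred term, AEs by grade, serious AEs, AEs leading to discontinuation, and AEs with an outcome of death.

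**The concern.** A between-arm test on related AEs is interpretable only if an event has the same opportunity to be called related in each arm. Here an Arm A event faces one causality question and an Arm B event faces two, with the results combined. If investigators attribute to TRC105 some events that they would not have attributed to axitinib, the related-AE proportion rises in Arm B without any extra toxicity. The trial is open label (Protocol 2.3.3), so the person attributing the event knows which drugs the patient is taking.

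The term study medication is also not defined for this comparison. If it means either drug, the asymmetry applies. If it means TRC105 alone, the Arm A count is zero by construction. Neither reading gives a fair contrast.

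The frequency and severity of AEs is a stated Phase 2 secondary objective. A small p-value on related AEs could be read as evidence of added toxicity when part or all of it comes from the additional attribution question.

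**Working it through.** The plan gives no AE rate, attribution rate, alpha or power for the safety comparisons, so there is no figure of its own to reproduce. What follows is an illustration.

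**Inputs from the documents.** About 150 patients randomized 1:1 (SAP 4.2), so 75 per arm. Chi-square or Fisher test (SAP 12.2). Attribution to either drug counts as related (Protocol 8.3.6).

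**Assumed inputs.** Two-sided 5% level. The same true incidence *p* of an AE in both arms. Probability *a* that an event is called axitinib-related, equal in both arms. Probability *t* that an Arm B event not called axitinib-related is called TRC105-related.

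**Formulas.**
- Related rate in Arm A = p × a
- Related rate in Arm B = p × [1 − (1 − a)(1 − t)]

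The rejection probability is found by exact enumeration of two binomials with n = 75 each, using the Pearson chi-square test.

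**Worked example, p = 0.50 and a = 0.20.** Arm A = 0.50 × 0.20 = 10%.
- t = 0: Arm B = 0.50 × (1 − 0.80 × 1.00) = 10%; rejection 5.1%.
- t = 0.05: Arm B = 0.50 × (1 − 0.80 × 0.95) = 12%; rejection 6.8%.
- t = 0.20: Arm B = 0.50 × (1 − 0.80 × 0.80) = 18%; rejection 29.4%.

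**Other combinations.**

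| p | a | t | Arm A | Arm B | Rejection |
|---|---|---|---|---|---|
| 0.4 | 0.9 | 0.3 | 36.0% | 37.2% | 5.4% |
| 0.4 | 0.5 | 0.3 | 20.0% | 26.0% | 13.9% |
| 0.4 | 0.5 | 0.5 | 20.0% | 30.0% | 29.1% |
| 0.6 | 0.3 | 0.5 | 18.0% | 39.0% | 82.2% |

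All-cause rates are equal by assumption (p against p), so the same test rejects at close to 5%: 5.5% at p = 0.4 and 5.5% at p = 0.5.

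The false-positive rate therefore runs from no inflation to large, depending almost wholly on how many events TRC105 attribution adds. It is small when most events are already called axitinib-related, and large when axitinib attribution is uncommon and TRC105 attribution is frequent.

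The model follows one AE type with one attribution per patient. The proportion of patients with any related AE combines several events, so its difference could be larger than shown or could vanish as both arms approach 100%. The figures show the mechanism and do not predict the result for the pooled category.

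**The case against.** Several points against the concern have force. The test sentence in SAP 12.2 is generic, follows the sentences on laboratory data and deaths, and does not single out related AEs. SAP 12 elsewhere describes the safety analysis as descriptive. The all-cause AE displays are planned by arm, so readers will have the unaffected comparison beside the related one. Counting an event related to any component is a legitimate description of a regimen's attributed toxicity. The primary endpoint is PFS, and the futility rule uses conditional power from the observed hazard ratio, so no decision depends on a related-AE p-value. These points stand and limit the severity. They do not repair the comparison: the sentence as written covers the related category, and the all-cause tables do not tell a reader how much of a related-AE difference comes from attribution.

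A reader might infer that the Arm B rate *is* inflated. The documents do not support that. If investigators merely double-label or reassign events they would have called axitinib-related anyway, the combined rate is unchanged, and Protocol 8.3.6 expressly allows dual attribution.

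A reader might also infer that a fixed share of Arm B related events exists only because of the second question. With independent attribution at equal probability *a* for each drug, that share is (1 − a)/(2 − a), which is 47% at a = 0.1 and 38% at a = 0.4. It follows entirely from assuming independence and equal probabilities, for which the documents give no basis.

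**Conclusion.** The point holds in a limited form. The two arms have different attribution rules, the pooled related category falls under an unrestricted between-arm test, and the Phase 2 table list lacks the by-drug split that would let a reader see the source of a difference. The related-AE comparison *can* be inflated in Arm B under identical all-cause toxicity.

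How far is unknown. With 75 per arm and an assumed two-sided 5% level, the illustration starts at about 5%, passes through 7% and 29%, and goes higher if TRC105 attribution adds many events. Severity is minor: the all-cause comparison is planned and sound, and nothing in the decision rules uses this p-value.

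**What to change.** In SAP 12.2 and Protocol 10.5.2:
- Define study medication for Phase 2.
- State that between-arm tests of AEs use all-causality treatment-emergent AEs.
- Present related AEs descriptively by drug, axitinib-related in both arms and TRC105-related in Arm B only, with no test on the pooled related category. The axitinib-related display should also stay descriptive, because an open-label investigator in Arm B can assign an event to TRC105 instead.

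In SAP 19.4, add tables 14.3.1.5 and 14.3.1.6 to the Phase 2 list.

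Attribution is already classified by drug under Protocol 8.3.6, so data collection, sample size and conduct do not change. The cost is the wording, two additional tables, and the loss of a p-value for pooled related AEs.

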12.3. Laboratory Evaluations

Quantitative laboratory test results and changes from baseline will be summarized at each visit for hematology, coagulation, serum chemistry panel, and urinalysis.

The Investigator will determine whether abnormal lab values are clinically significant. Such results are to be reported as adverse events and CTCAE grading will be assigned (except for urinalysis) where applicable.

Laboratory results that are abnormal and clinically significant will be flagged by the investigator. Abnormal and clinically significant results will be presented in listings with Investigator comments.

The number and percentage of patients who exhibit clinically significant abnormal laboratory results will be produced at each visit.

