This is a phase 2, randomized, open label study of axitinib alone versus TRC105 plus axitinib including a lead-in phase 1b dose escalation study of axitinib in combination with TRC105. The phase 1b portion is a standard “3+3” dose-escalation design of patients with advanced RCC followed by an expanded cohort to further assess the safety and tolerability of the recommended phase 2 dose (RPTD) of TRC105. The purpose of the dose escalation portion is to determine the maximum tolerated dose (MTD) of TRC105 with axitinib and determine the dose limiting toxicities. Patients included in the phase 1b portion of the study will have RCC that has progressed following VEGFR TKI treatment. Secondary endpoints will be progression free survival (PFS) and response rate (RR), safety, and correlative studies of plasma angiogenic biomarkers. The maximum tolerated dose from the phase 1b portion will be studied in the phase 2 portion. The phase 2 portion is a multicenter, randomized, phase 2 study of TRC105 in combination with standard dose axitinib versus axitinib alone in patients with advanced or metastatic renal cell carcinoma. Patients will be stratified by performance status (PS = 0 vs. PS = 1) and centrally randomized in a 1:1 ratio to one of the following treatment arms: TRC105 in combination with standard dose axitinib vs. standard dose axitinib, following documented progression on one prior VEGFR TKI. The primary endpoint is PFS and secondary endpoints will evaluate safety, immunogenicity and correlative studies of plasma angiogenic biomarkers.

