2.3.6. Potential Risks and Benefits to Human Patients

2.3.6.1. Potential Risks

TRC105

Grade 3 anemia has occurred with TRC105 therapy at the recommended phase 2 dose. All patients treated with TRC105 should be monitored closely for anemia and treated appropriately, including the possibility of TRC105 dose reductions. Anemia may be caused by correctable mineral or vitamin deficiency. The anemia related to TRC105 is hypoproliferative in nature and is reversible with interruption of treatment, transfusion, erythropoietin, and other interventions as appropriate.

Gastrointestinal hemorrhage has occurred with TRC105 therapy. Patients with active ulcer disease or risk factors for ulcer disease are excluded from this study.

Grade 1 and 2 cutaneous telangiectasia related to TRC105 occur early in the course of therapy and have been the source of gingival bleeding and epistaxis. Telangiectasia are also seen in patients with hereditary hemorrhagic telangiectasia (HHT), a disease of CD105 haplotype insufficiency. Patients with HHT are at risk of hemorrhage from abnormal blood vessels and this could be exacerbated by treatment with TRC105. Other contraindications to TRC105 therapy include a history of significant hemorrhage or tumors located in the central chest or another location where bleeding is associated with high morbidity. All patients treated with TRC105 should be monitored for signs of hemorrhage and the risks and benefits of drug treatment reevaluated in any patient with hemorrhage.

Premedication including the use of glucocorticoid is required prior to infusion of TRC105 to reduce the frequency and severity of infusion reactions. Infusion reactions following TRC105 dosing generally occur with the first TRC105 dose and include a grade 4 vasovagal reaction that resolved without sequelae. Signs and symptoms of TRC105 infusion reactions include hypertension, hypotension, dyspnea, bronchospasm, chills/rigors, chills, sweats, fever, nausea, tachycardia, bradycardia, EKG changes, flushing, urticaria, pruritus, and headache, generally of

grade 1 and 2 severity. Potential infusion reactions seen with other therapeutic antibodies include angioedema, asthenia, throat irritation, rhinitis, vomiting, joint pain, fatigue and neurologic disorders including inflammation of the spine and/or brain.

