8.1.1. Laboratory Safety Assessments

Abnormal and clinically significant laboratory tests should be recorded as adverse events. To meet the definition of clinically significant, the test result generally requires a change in medical management (e.g. new medication, unplanned treatment, additional tests, etc.).

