8.2.1. Definition of Adverse Event

An adverse event is any untoward medical occurrence in a trial patient who is administered a drug or biologic (medicinal product); the event may or may not have a causal relationship with the medicinal product. Examples of adverse events include, but are not limited to the following:

- Clinically significant symptoms and signs including:
 - Worsening of signs and symptoms of the malignancy under trial (disease progression without worsening of signs and symptoms assessed by measurement of malignant lesions on radiographs or other methods should not be reported as adverse events).
 - Signs and symptoms resulting from drug overdose, abuse, misuse, withdrawal, sensitivity, dependency, interaction or toxicity.
 - All possibly related and unrelated illnesses, including the worsening of a preexisting illness.

-
- Injury or accidents. Note that if a medical condition is known to have caused the injury or accident (hip fracture from a fall secondary to dizziness), the medical condition (dizziness) and the outcome of the accident (hip fracture from a fall) should be reported as 2 separate adverse events.
 - Symptoms or signs resulting from exposure *in utero*.
 - Abnormalities in physiological testing or physical examination findings that require clinical intervention or further investigation (beyond ordering a repeat confirmatory test).
 - Laboratory abnormalities that meet any of the following (Note: merely repeating an abnormal test, in the absence of any of the below conditions, does not constitute an adverse event. Any abnormal test result that is determined to be an error does not require reporting as an adverse event.):
 - Test result that is associated with accompanying symptoms
 - Test result that requires additional diagnostic testing or medical/surgical intervention
 - Test result that leads to a change in TRC105 study drug dosing not stipulated in the protocol or discontinuation from the trial, significant additional concomitant drug treatment, or other therapy
 - Test result that is considered to be an adverse event by the Investigator or TRACON

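### Incidence and CTCAE grade of laboratory abnormalities, including anemia, come only from values an open-label investigator calls clinically significant; no grade or shift table is derived from the numeric results

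*SAP*

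**What the plan says.** SAP 12.3 treats laboratory data in two layers.

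- **Numeric.** Quantitative results and changes from baseline are summarized at each visit. SAP 12.2 gives these for each arm and names the Student t test for continuous variables. SAP 20.3 plans by-arm figures over time for hemoglobin, white cells, platelets and chemistry.
- **Graded and counted.** "The Investigator will determine whether abnormal lab values are clinically significant". The next sentence reads: "Such results are to be reported as adverse events and CTCAE grading will be assigned (except for urinalysis) where applicable". The section ends: "The number and percentage of patients who exhibit clinically significant abnormal laboratory results will be produced at each visit". SAP 12.2 summarizes clinically significant laboratory abnormalities by study arm and names chi-square or Fisher tests for categorical comparisons.

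Protocol 8.1.1 gives a partial definition: "To meet the definition of clinically significant, the test result generally requires a change in medical management". Protocol 8.2.1 lists when a laboratory result counts as an adverse event and ends with an open criterion: "Test result that is considered to be an adverse event by the Investigator or TRACON". Protocol 2.3.3 describes the design: "This is a phase 2, randomized, open label study of axitinib alone versus TRC105 plus axitinib". Protocol 8.1 says that CTCAE severity, among other attributes, will characterize both adverse events and laboratory abnormalities.

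**The concern.** Two patients with the same hemoglobin can be handled differently. If the investigator calls one value clinically significant and not the other, only the first is graded and counted. The investigator knows the arm and has been told what to expect. Protocol 2.3.6.1 states: "Grade 3 anemia has occurred with TRC105 therapy at the recommended phase 2 dose". It asks for close monitoring of TRC105 patients for anemia, with TRC105 dose reduction as one possible response. Since clinical significance generally means a change in management, and changing TRC105 is possible only in Arm B, the same value may prompt action in one arm and not in the other.

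A secondary objective is the frequency and severity of adverse events by CTCAE. How many patients in each arm reached grade 3 anemia is a safety result readers will look for, and means and changes from baseline do not answer it. Blood counts and chemistry are already collected (Protocol 8.1.1.1), so many grades could be computed from the numbers.

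**Working it through.** The documents state no sample size, power or alpha for the laboratory comparison, so there is no figure of the plan to reproduce. The check is mainly textual, followed by an illustration.

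**1. Which displays depend on the investigator's call?**

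| Display | Source | Depends on the call? |
|---|---|---|
| Values and change from baseline, by arm | SAP 12.2, 12.3 | No |
| Hemoglobin and chemistry figures by arm | SAP 20.3 | No |
| Count and percentage of patients with clinically significant results, per visit | SAP 12.3 | Yes |
| Clinically significant laboratory abnormalities by arm | SAP 12.2 | Yes |
| Laboratory events in adverse event tables by maximum CTCAE grade | SAP 12.2, 19.4 | Yes |
| Grade, worst grade or shift table computed from numeric results | None found in SAP 12.2, 12.3, 19.3, 19.4, 20.2 or 20.3 | Not planned |

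Protocol 8.1 is therefore broader than what the SAP grades. The phase 2 list in SAP 19.4 also lacks the laboratory change-from-baseline tables that SAP 19.2 lists for phase 1b.

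**2. Sampling.** Hematology is scheduled on days 1 and 15 of cycles 1 and 2 in both arms. From cycle 3 it is scheduled on day 1 only in Arm A (Table 9), but on days 1 and 15 in Arm B (Tables 10 and 11). Scheduled draws over six cycles:

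- Arm A: 2×2 + 4×1 = 8
- Arm B: 2×2 + 4×2 = 12

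Chemistry days match across arms. The extra draws can raise cumulative adverse event or worst-grade counts for hematology in Arm B. They do not inflate a per-visit percentage.

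**3. Illustration of what differential flagging could do.** From the documents: about 150 patients randomized 1:1 (SAP 4.2), so n = 75 per arm. Also from the documents: anemia reported in 9 of 19 patients = 47% at 10 mg/kg with bevacizumab (Protocol 2.3.2.1), used only as an upper value. Assumed: the true rates, the flagging probabilities and a two-sided 0.05 test.

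Observed rate = true rate × probability of being flagged.

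Chance of a nominally significant result = Φ[(d − 1.96·se0)/se1], where d is the absolute difference between the observed rates p1 and p2, p̄ is their mean, se0 = √(2p̄(1−p̄)/n) and se1 = √([p1(1−p1) + p2(1−p2)]/n).

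Worked case, true rate 30% in both arms, flagged 50% (A) and 80% (B):

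- p1 = 0.30×0.50 = 0.15; p2 = 0.30×0.80 = 0.24; d = 0.09; p̄ = 0.195
- se0 = √(2×0.195×0.805/75) = 0.0647
- se1 = √((0.1275 + 0.1824)/75) = 0.0643
- Φ[(0.09 − 1.96×0.0647)/0.0643] = Φ(−0.57) = 0.28

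No true difference:

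| True rate, both arms | Flagged A / B | Observed A / B | Nominally significant |
|---|---|---|---|
| 20% | 60% / 80% | 12% / 16% | 10% |
| 20% | 50% / 80% | 10% / 16% | 19% |
| 30% | 60% / 80% | 18% / 24% | 14% |
| 30% | 50% / 80% | 15% / 24% | 28% |
| 47% | 60% / 80% | 28.2% / 37.6% | 23% |
| 47% | 50% / 80% | 23.5% / 37.6% | 47% |

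Swapping the flagging rates between arms gives the same chances in the opposite direction.

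True difference of 25% (A, assumed) versus 47% (B):

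| Flagged A / B | Observed A / B | Power |
|---|---|---|
| 100% / 100% | 25% / 47% | 81% |
| 80% / 80% | 20% / 37.6% | 67% |
| 60% / 60% | 15% / 28.2% | 50% |
| 80% / 60% | 20% / 28.2% | 21% |

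Flagging can thus create a difference or hide one.

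**The case against.** The strongest reply is that the plan already contains an objective laboratory comparison. Numeric values and changes are summarized by arm, and hemoglobin is plotted by arm. Phase 2 also has listings of abnormal laboratory results. This stands. A reader might infer that the whole between-arm laboratory comparison rests on judgement; the documents do not support that. Only incidence and grade do.

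Second, the call is not unconstrained. Protocol 8.1.1 ties it to a change in management. Protocol 8.2.1 adds accompanying symptoms, further testing or intervention, and significant added treatment, and lets the sponsor as well as the investigator designate an event. Anemia that is transfused would qualify in either arm, so differential flagging is more plausible for milder values. This also stands, but no numeric cut-off is set and the criteria still turn on what the investigator does.

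Third, adverse events are investigator-reported by design, and the secondary objective concerns adverse events, not every abnormal value. That is fair, and it is why the adverse event tables should keep their place. It does not cover Protocol 8.1, which names laboratory abnormalities separately.

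Fourth, a reader might take the unequal day 15 blood counts as biasing the table in SAP 12.3. They do not: that table is per visit, so day 1 can be compared with day 1. The imbalance matters for cumulative counts.

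Last, the flagging rates used above are pure assumption. That is correct; they show mechanism and range, not an estimate.

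**Conclusion.** The point holds for the incidence and CTCAE grade of laboratory abnormalities, including anemia. These are taken only from values that an open-label investigator calls clinically significant, and nothing planned derives a grade from the numeric results. The numeric summaries are not affected.

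The documents do not show the size or direction of any flagging difference. Under the assumed settings with no true difference and 75 patients per arm, the chance of a nominally significant result runs from 10% to 47%, against a nominal 5%. If a true difference of 25% versus 47% exists, power falls from 81% to between 67% and 21%.

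This is a weakness in safety reporting. It touches neither the primary PFS analysis nor any decision rule. It is worth correcting because the remedy uses data already collected and depends less on who makes the call.

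**What to change.** In SAP 12.3 and the phase 2 table list (SAP 19.4):

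- Assign CTCAE 4.0 grades by program to hematology and chemistry results that can be graded from numbers, and add baseline-to-worst-grade shift tables by arm. Place these beside the investigator-reported adverse event tables, not instead of them.
- Show worst grade in two ways: on visits scheduled in both arms (day 1 of each cycle, day 15 of cycles 1 and 2), and on all available results. The first removes the hematology sampling imbalance; the second avoids discarding Arm B day 15 and unscheduled values.
- Report transfusion and erythropoietin use by arm next to the hemoglobin grades, because both can mask falls.
- List the laboratory change-from-baseline tables for phase 2 as for phase 1b.

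The cost is SAP wording and some standard extra programming, with no new data collection. One limit remains: CTCAE criteria that need clinical information cannot be graded from numbers alone, so the adverse event tables are still needed for those.
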